#### Hypothesis for Aim 1:

1.1 – PN containing Omegaven™ will be safe for patients with respect to the risk of unexpected bleeding, coagulopathies, and other adverse events.

1.2 – PN containing Omegaven™ will promote more short-term growth and development than conventional fat emulsions.

1.3-Incidence of sepsis will be similar to historical incidence of sepsis on TPN and IL™

2. To determine if established PN associated liver disease can be reversed or its progression halted by using a parenteral fat emulsion prepared from fish oil as measured by normalization of serum levels of hepatic enzymes and bilirubin.

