## 4.0 Inclusion/Exclusion Criteria

### Inclusion Criteria:

1. Patients aged 0 to 2 years will be PN dependent (unable to meet nutritional needs solely by enteral nutrition) and are expected to require PN for at least another 30 days
2. Patients considered eligible for study participation must have parenteral nutrition associated liver disease (PNALD) as defined as a direct bilirubin of >2.5 mg/dl or more. Other causes of liver disease should be excluded. A liver biopsy is not necessary for treatment.
3. Signed patient informed consent.

4. The patient must have utilized standard therapies to prevent the progression of his/her liver disease including surgical treatment, cyclic PN, avoiding overfeeding, reduction/removal of copper and manganese from PN, advancement of enteral feeding, and the use of ursodiol (i.e., Actigall®).

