## **10.0 Statistical Considerations**

### ***Analysis of Safety and Tolerability of Omegaven™***

All primary safety and tolerability analyses will be based on descriptive statistics. In secondary analyses, we will also assess the statistical significance of differences. Some safety and tolerability outcomes will be measured only in the Omegaven™ group. For those, we will compare results before starting PN with Omegaven™ (while receiving PN with soybean oil fat emulsions) with after starting PN with Omegaven™. The period receiving Omegaven™ will start to be counted 30 days after beginning PN with Omegaven™ for the main analysis.

Primary outcomes measured in the Omegaven™ group will include routine measurement of the direct bilirubin levels and whether the INR was ever  $> 2$ .

Primary outcomes measured in the Omegaven™ and soybean based fat emulsion groups will include whether triglycerides were ever  $> 400\text{mg/dL}$ , whether albumin was ever  $> 3$ , any occurrence of unexpected bleeding and number of times it occurred, occurrence of any anaphylactic reaction, rate of blood stream infections as shown by positive blood cultures, rate of line infections and gram positive central venous catheter infections..

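### The before/after comparison of INR ever above 2 has no fixed period lengths and no denominator, so it mixes coagulation risk with the number of INR tests

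*Combined protocol and SAP*

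**What the plan says.** Section 10.0, Analysis of Safety and Tolerability, lists among the primary outcomes of the Omegaven group "whether the INR was ever" above 2. It keeps this apart from the outcomes measured in both the Omegaven and soybean groups. For outcomes measured only in the Omegaven group, "we will compare results before starting PN with Omegaven™ (while receiving PN with soybean oil fat emulsions) with after starting PN with Omegaven™". That INR falls under this rule is an inference, but it is the natural reading.

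On timing: "The period receiving Omegaven™ will start to be counted 30 days after beginning PN with Omegaven™ for the main analysis". On method: "All primary safety and tolerability analyses will be based on descriptive statistics". Significance of differences is left to secondary analyses, with no test named.

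Other sections bear on how many INRs each period can hold:

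- **Section 6.0, Tables 2 and 3** (both titled as suggested schedules) give one baseline INR and repeated INRs on treatment. Table 2 ticks INR under *Biweekly* beneath a caption that says weekly until a direct bilirubin limit is reached. Table 3 ticks it under *Q week*. Table 3's footnote lets frequency rise or fall with clinical course.
- **Section 6.0, Data Collection** takes all clinical and laboratory data from medical records, so any earlier soybean-period INR would come from the chart.
- **Section 6.0, Duration of Therapy** ties treatment to weaning from PN, and allows Omegaven to continue after the rest of PN stops.
- **Section 4.0** requires that the infant is "expected to require PN for at least another 30 days".

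The hypothesis for Aim 1 is safety "with respect to the risk of unexpected bleeding, coagulopathies, and other adverse events".

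**The concern.** An *ever* outcome counts an infant once if any test crosses the threshold. Its probability therefore depends on how often the infant is tested as well as on risk. The plan sets neither period's length and does not say whether the denominator is infants with at least one INR, tests, or time.

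INR is the laboratory outcome that bears most directly on coagulopathy in Aim 1, and the primary analysis is descriptive, so the table is itself the result. If the Omegaven period holds more tests, the table can suggest harm that is not there. If the soybean period holds more, it can hide harm.

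The day-30 rule adds two difficulties. A high INR in days 0–29 falls outside the main analysis. And an infant who stops near day 30 may have no counted INR; the plan does not say whether that infant is coded as never above 2 or as not assessable.

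**Working it through.** The plan states no INR rate, sample size or alpha, so there is no figure to reproduce. The check asks what the planned comparison shows when the drug has no effect.

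**Inputs.** From the documents: one scheduled INR before treatment, repeated INRs after, counting from day 30, and 13 infants (the count in section 7.0; no final size is stated). Assumed: per-test risk *p*, tests per period *k*, within-infant correlation (ICC), and a two-sided level of 0.05.

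**Step 1: probability of ever exceeding 2.** With independent tests, P(ever) = 1 − (1 − p)^k. With correlation, a beta-binomial is used, with a = p(1 − ICC)/ICC and b = (1 − p)(1 − ICC)/ICC. For p = 0.02 and k = 4, ICC 0: 1 − 0.98^4 = 7.8%. For k = 12: 1 − 0.98^12 = 21.5%.

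| ICC | 4 tests | 8 tests | 12 tests | Ratio, 4 before and 12 after | Ratio, 8 before and 4 after |
|---|---|---|---|---|---|
| 0 | 7.8% | 14.9% | 21.5% | 2.77 | 0.52 |
| 0.3 | 5.2% | 7.5% | 9.0% | 1.71 | 0.70 |
| 0.5 | 4.1% | 5.3% | 6.0% | 1.47 | 0.77 |

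Ratios are after over before. At p = 0.01 or 0.05 they run from 1.45 to 2.88 and from 0.51 to 0.78. For 13 infants at p = 0.02, 4 versus 12 tests means 13 × 0.078 = 1.0 versus 13 × 0.215 = 2.8 infants at ICC 0, and 0.5 versus 0.8 at ICC 0.5.

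**Step 2: what the table would show.** In 13 infants at p = 0.02 with no drug effect, 4 versus 12 tests gives more infants above 2 after than before in 77%, 43% or 26% of trials (ICC 0, 0.3, 0.5), and fewer in 9%, 7% or 5%. With 8 versus 4 tests it gives fewer after in 60%, 34% or 21%, and more in 18%, 11% or 7%.

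**Step 3: the secondary test.** The plan names none; exact McNemar is assumed. Rejection rates for 13 infants with no drug effect:

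| Risk per test | ICC | 1 vs 12 tests | 4 vs 12 tests |
|---|---|---|---|
| 2% | 0 | 3.4% | 1.7% |
| 2% | 0.3 | 0.02% | 0.001% |
| 5% | 0 | 42.7% | 14.7% |
| 5% | 0.3 | 1.2% | 0.1% |
| 10% | 0.3 | 13.8% | 1.2% |

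**Step 4: the day-30 rule.** Suppose tests fall on days 7, 14, … or 14, 28, …. Days 0–29 then hold 4 weekly INRs (7, 14, 21, 28) or 2 two-weekly INRs (14, 28), none of them counted. The first counted INR is on day 35 (weekly) or day 42 (two-weekly). An infant who stops on days 30–34, or up to day 41 on the two-weekly reading, has no counted scheduled INR on drug. If 3 of 13 infants (assumed) were in that position and coded as never, a true 7.5% would be reported as 7.5% × 10/13 = 5.8%.

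**The case against.** **The periods are not unbounded.** The before period is time on soybean-oil PN and the after period is time on Omegaven from day 30. A reader might infer that the plan sets no look-back and no end at all; that goes too far. What is missing is a fixed length, a stated rule for INRs drawn after Omegaven stops, and a denominator.

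**The imbalance is not demonstrated.** The scheduled tests alone favour more INRs on drug, but a long charted soybean period could reverse this. A reader might infer that the plan is biased towards showing harm; the documents do not support a direction. At ICC 0.5 the 4-versus-12 effect in 13 infants is only 0.5 versus 0.8 infants.

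**The secondary tests.** One might infer that 13 infants are too few for false positives, or that the tests are plainly inflated. Neither follows. Step 3 runs from far below 5% to 42.7% depending on assumptions that the documents do not settle, and 13 is a count at the time of writing, not a final size.

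**A rate is not a full cure.** If testing follows illness, as Table 3's footnote allows, a rate per tested week is also biased. As an illustration with all figures assumed, take 20% ill weeks, risk 10% when ill and 0.5% when well, all ill weeks tested and 20% of well weeks tested. The rate is (0.2 × 0.10 + 0.16 × 0.005)/0.36 = 5.8%. Testing every week would give 0.2 × 0.10 + 0.8 × 0.005 = 2.4%. This stands as a limit of the fix.

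**Bleeding is a different comparison.** Unexpected bleeding is in the two-group list and should not be read as part of the within-infant INR problem. It has its own gap: it is given as "any occurrence of unexpected bleeding and number of times it occurred" with no person-time, while infections are given as "rate of blood stream infections as shown by positive blood cultures".

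**The schedule.** The contents list a study procedure calendar as Appendix A that is not in the text available here; it may settle the INR frequency. Tables 2 and 3 still need reconciling.

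**Conclusion.** The point holds and should be fixed. As written, the before/after INR figures mix risk with number of tests, and infants without a counted INR can be taken for infants without an event. With no drug effect and 2% risk per test, the after/before ratio is 1.5 to 2.8 for 4 versus 12 tests, and 0.52 to 0.77 for 8 versus 4. Correlation within infants shrinks the artefact but does not remove it. All rates, test counts and correlations are assumptions. The direction depends on how many soybean-period INRs the charts hold, and whether the secondary tests are inflated remains open. Study conduct is not affected; the interpretation of one primary safety comparison is.

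**What to change.** 1. **Main comparison.** Use weeks with any INR above 2 divided by weeks with at least one INR, per infant and pooled. Use observed time in each period up to a stated maximum: for example, up to 2 months before baseline (or from birth if shorter), and from day 30 up to 2 months or the end of Omegaven. The 2-month look-back already appears in the efficacy section for graphical profiles. Partly observed windows contribute the time they have, because a full 2 months from day 30 needs about 90 days on drug, whereas eligibility requires only 30 further expected days of PN. Report tests and weeks for each infant and period.
2. **Secondary tests.** Apply any significance test to these rates, not to the *ever* indicator.
3. **Untested infants.** Show an infant with no INR in a period as not assessable, with the reason.
4. **Early events.** Keep *ever above 2* as description over all time on drug, and tabulate days 0–29 separately.
5. **Sensitivity and limits.** Repeat with scheduled tests only for the on-drug period. State that illness-triggered testing, age and disease progression remain confounded with period. Reconcile the INR frequency in Tables 2 and 3.
6. **Bleeding, separately.** In the two-group outcomes, report unexpected bleeding per patient-week.

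The cost is SAP wording, a little more analysis and dated INRs from the charts; no new tests are needed. The main comparison uses less data, and the rate stays biased if soybean-period INRs were drawn mainly during illness.

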## Details of Omegaven™ Administration

After baseline labs are obtained (Table 2 and 3), therapy with Omegaven™ will be initiated at the goal dose of 1 gram /kg/day and is infused over 12-24 hours. Omegaven™ will be infused intravenously through either a central or peripheral catheter alone or in conjunction with parenteral nutrition. If additional fat calories are needed, they will be provided via the enteral route.. The same standards of care provided to all patients receiving parenteral nutrition solution will be followed. Routine nutritional monitoring is described in Table 3.

Table 2: Suggested Schedule Safety Monitoring for Omegaven™ Therapy

(To be done baseline pre-Omegaven™ therapy and weekly until direct bilirubin <0.4 mg/dL)

Parameter	Baseline	Biweekly	Monthly
Essential Fatty Acid Profile	X		X
PT	X	X	
PTT	X	X	
INR	X	X	

Table 3: Suggested Monitoring Schedule for Omegaven™ Therapy  
(Amended December 26, 2006)

Parameter	Baseline (pre- Omegav- en)	Dail y	Q week * -	Periodicall y**
Weight	X	X		
Fluid balance	X	X		
Vital Signs	X	X		
Catheter site/function	X	X		
Laboratory test:				
Sodium	X		X	
Potassium	X		X	
Chloride	X		X	
Glucose	X		X	
BUN	X		X	
Creatinine	X		X	
Triglycerides	X		X	
Calcium	X		X	
Magnesium	X		X	
Phosphorus	X		X	
Prealbumin	X		X	
C reactive protein	X		X	
Albumin	X		X	
Total protein	X		X	
SGPT	X		X	
Alkaline phosphatase	X		X	
Bilirubin (total and direct)	X		X	

GGT	X		X	
AST	X		X	
Copper				X
Iron				X
Vitamins A,D,E				X
Essential Fatty Acid Profile	X		X	
Free cholesterol	X		X	
Free fatty acids	X		X	
Lipid Panel	X		X	
Hemoglobin	X		X	
Hematocrit	X		X	
RBC	X		X	
WBC	X		X	
Platelets	X		X	
PT	X		X	
PTT	X		X	
INR	X		X	
Fibrinogen				
Selenium				X
Zinc				X
Carnitine				X
Aluminum				X
Retinol binding protein (check when getting Vit A)				X

\* More often as necessitated by clinical course; may be reduced in patients who are stable and whose biochemical markers have improved. Refer to protocol for additional information

In the event that a patient is unable to achieve adequate calories parenterally and is unable to tolerate enteral feeds, it may be necessary to evaluate whether or not the patient should continue the study with Omegaven™ as monotherapy or resume therapy with conventional fat emulsions so that additional parenteral fat calories can be given. The clinical team, in conjunction with the patient's primary physician, will determine if the patient should be removed from the protocol. The DSMB will also be notified.

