#### Duration of Therapy

Patients will remain on Omegaven™ until weaned from PN. Patients may continue monotherapy with Omegaven™ as an additional source of calories after the dextrose/protein portion of PN is discontinued

In the event that a patient who has been listed for a liver or liver/intestinal transplant has an organ become available, the participation in this protocol will not preclude them from receiving the transplant.

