### ***Analysis of Efficacy of Omegaven™***

The primary outcome to gain preliminary evidence of efficacy will be based on the time from baseline to normalization of bilirubin level, i.e, first time point among three consecutive in which bilirubin is  $< 2\text{ mg/dL}$ . We do not anticipate that any subject will present a rebound on direct bilirubin after normalization. However, we will describe the cohort with respect to the frequency of rebounds in bilirubin levels.

Crude comparisons of time to normalize direct bilirubin levels using Omegaven™ Results of these analysis will be compared with results of analysis excluding subjects who die or are transplanted. Time to reach a total bilirubin of 1.2 will also be compared using survival analysis methods. Analysis of this outcome will proceed as described for direct bilirubin.

We will also describe individual profiles over time (i.e., 2 months before baseline or birth until end of follow-up period) for all subjects using graphical methods. Trends in liver function markers over time will be explored using generalized linear models in which correlations of observations within subjects will be accounted using a generalized equations or random effects approach. In these models we will hypothesize that for both groups biochemical levels increase for all tests with equal slope before treatment. After treatment, however, levels should be decreasing for patients in the Omegaven™ group. We will perform these analyses including only subjects who did not die or undergo transplantation and including all subjects but assigning for subjects who died or underwent a transplant their worse possible outcome after they died or had the transplant. Using descriptive statistics, we will also explore the association between spikes in blood tests over time and predictors including transfusions of red blood cell products and blood stream infections.

Assessment of efficacy will be also based on comparison of means (or medians) of the mean and maximum modified PELD scores of each subject across all follow-up weeks. Adjustments of these comparisons for potential confounders will be based on linear regression models. Mean rates of infection will be compared. Liver transplant, mortality, and red blood cell product transfusion events will be collected.

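### The main before/after safety comparison counts Omegaven time only from day 30, so an INR above 2 in the first 30 days falls in neither period

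*Combined protocol and SAP*

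**What the plan says.** Section 10.0, Analysis of Safety and Tolerability, makes the primary safety analyses descriptive. Some outcomes are measured only in the Omegaven group: "For those, we will compare results before starting PN with Omegaven™", on soybean emulsion, with results after starting it. The next sentence sets the window: "The period receiving Omegaven™ will start to be counted 30 days after beginning PN with Omegaven™ for the main analysis". The outcomes named for the Omegaven group alone are "routine measurement of the direct bilirubin levels and whether the INR was ever" above 2. A separate list covers outcomes measured in both the Omegaven and soybean groups: triglycerides, albumin, unexpected bleeding, anaphylaxis and infections.

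Elsewhere in the same document:

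- Section 8.0 assesses and reports adverse events from the first infusion.
- Section 6.0, Details of Omegaven Administration: "therapy with Omegaven™ will be initiated at the goal dose of 1 gram /kg/day".
- Section 6.0, Duration of Therapy: "Patients will remain on Omegaven™ until weaned from PN". It adds that Omegaven alone may go on once the dextrose and protein part has stopped.
- Section 4.0 admits infants who "are expected to require PN for at least another 30 days".
- Section 9.0 allows withdrawal at any time, including for toxicity or transplant.

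**The concern.** Aim 1 is the safety profile, and hypothesis 1.1 names coagulopathies. INR above 2 is the only coagulation laboratory outcome named in Section 10.0. Because the primary safety analysis is descriptive, the choice of which results to count largely determines what is reported.

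The window rule removes the first 30 days on drug from the main comparison of that outcome. This does not fit an outcome defined as INR *ever* above 2, or adverse event assessment from the first infusion. Treatment starts at the goal dose, so a titration phase does not explain the lag. The text gives no other reason, names no safety analysis from day 0, and does not mention the lag under Limitation of Study.

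The lag also restricts the after period to infants still on Omegaven past day 30. Infants withdrawn earlier, including for toxicity, drop out of it.

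**Working it through.** The plan gives no sample size, event rate or treatment length for this point, so there is no figure of its own to reproduce. The check is of period boundaries and simple counts.

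**1. The gap.** Let day 0 be the start of Omegaven (Section 10.0).
- Before period: ends at day 0.
- Counted Omegaven period: starts at day 30.
- Gap: 30 − 0 = 30 days. An INR above 2 on day 10 is on drug but belongs to neither period.

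**2. Infants with no after data.** For an infant on Omegaven for T days, counted days = max(0, T − 30). This is 0 for any T up to 30. Examples are an infant withdrawn under Section 9.0 by day 30, or one weaned by then who does not continue on Omegaven alone. The expected further PN need at entry is at least 30 days, the same length as the lag, so such infants should not be typical.

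**3. INR draws in the gap, per infant treated to day 30.** The Table 2 heading says "weekly until direct bilirubin <0.4 mg/dL", and Table 3 also lists INR weekly. The Table 2 column for INR is biweekly, which can mean two things.
- Weekly: days 7, 14, 21, 28 = 4 draws.
- Every two weeks: days 14, 28 = 2 draws.
- Twice weekly (every 3.5 days up to day 28): 28 / 3.5 = 8 draws.

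Both tables are suggested schedules, so these counts assume that they are followed.

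**4. Scale in the cohort so far.** Section 7.0 mentions 13 infants, which is a count to date and not a target. If all were treated to day 30, the gap holds 13 × 30 = 390 infant-days and 13 × 4 = 52 weekly draws (range 13 × 2 = 26 to 13 × 8 = 104).

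**5. Share of on-drug time uncounted.** For T of at least 30 days, share = 30 / T. T is assumed, because the plan fixes no length.

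| Assumed T (days) | Uncounted share | Counted days |
|---|---|---|
| 30 | 100% | 0 |
| 45 | 67% | 15 |
| 60 | 50% | 30 |
| 90 | 33% | 60 |
| 180 | 17% | 150 |

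Steps 3 to 5 count time and tests, not events. They do not measure bias.

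**6. Unequal windows.** If each test had the same chance p of exceeding 2, independently, the chance of at least one exceedance in n tests would be 1 − (1 − p)^n, which rises with n. Section 10.0 does not say how long the before period is for INR. Moving the start to day 0 therefore does not by itself make the two periods comparable. Denominators are needed too.

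**The case against.** The strongest reply is that little is lost. Early events are still recorded and reported under Section 8.0, and Section 9.0 keeps results up to withdrawal. No test or decision rule depends on the window. The statement about INR ever above 2 can be read as a separate, unlagged outcome. Limiting the lag to the main analysis implies that others may differ. A lag could also be meant to limit carry-over from the soybean emulsion. Individual profiles planned under Analysis of Efficacy span the first 30 days.

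Most of this stands and limits the severity. It does not close the gap. Adverse event reporting does not put an early INR into the main comparison. The text does not say that the INR outcome is unlagged, no other safety analysis is named, and carry-over is not stated as the reason. The profiles sit under efficacy and do not name INR.

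A reader might infer three stronger things that the documents do not support:

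- **That the first month counts towards benefit but not harm.** The primary efficacy outcome "will be based on the time from baseline to normalization of bilirubin level". That is a time-to-event clock, so infants not yet normalized in the first 30 days accrue time against Omegaven. The before/after lag also covers direct bilirubin, so it does not single out harm.
- **That early bleeding, anaphylaxis, high triglycerides and infections are excluded as well.** The lag sentence directly follows the before/after comparison of Omegaven-only outcomes, while these are two-group outcomes. The wider reading is not ruled out, but it is the less likely one.
- **That any infant weaned at day 30 contributes nothing.** Omegaven may continue alone after the rest of PN stops. Only an infant whose Omegaven itself ends by day 30 is lost.

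**Conclusion.** The concern holds for the before/after comparison of Omegaven-only outcomes, and matters chiefly for INR. As written, the main analysis leaves INR above 2 in the first 30 days out of both periods and has no after data for infants whose Omegaven stops by day 30. The rule is stated without a reason, and it is at odds with the word *ever* and with adverse event assessment from the first infusion.

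The size of the effect on the result is unknown, because neither event rates nor treatment lengths are given. What can be said is that about 4 INR draws go uncounted per infant treated to day 30 if the suggested weekly schedule is followed, or 2 or 8 under the two readings of the biweekly column. The loss of early withdrawals is possible but also of unknown size: moderate or severe adverse events that may be related usually lead to a temporary halt, although anaphylactic or allergic reactions end treatment.

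This should be fixed, but it is not critical: the analyses are descriptive and early events are still reported.

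**What to change.** In Section 10.0, Analysis of Safety and Tolerability, replace the lag sentence with text to this effect:

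> In the main analysis, INR above 2 is counted from the first Omegaven infusion in every treated infant, and is shown with the number of infant-days or INR tests in the before and after periods. A before/after comparison that starts the Omegaven period at day 30 is secondary. Its reason is stated, and the number of infants with under 30 days of Omegaven is reported beside it. The lag does not apply to triglycerides, albumin, unexpected bleeding, anaphylactic reactions or infections.

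The denominators are needed because an *ever* outcome depends on how long and how often infants are tested. If carry-over from the soybean emulsion is the reason for the lag, the plan should say so.

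The cost is a few sentences and no new data, since INR is already scheduled from baseline and adverse events are assessed from the first infusion. The downside is that reported INR counts may be less favourable, and early values may partly reflect carry-over. The labelled secondary analysis can show how much the lag changes the picture.

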#### Dose Modification

#### Lipid Intolerance

If lipid intolerance develops, defined as serum triglyceride levels > 200 mg/dL, the following will be considered prior to reducing the dose:

a) If the level was obtained while the patient was receiving a continuous 24- hour infusion of Omegaven™, the total dose should be infused over 20 hours, and a repeat serum triglyceride level obtained prior to resuming the infusion 4 hours later.

b) Other sources of lipid intolerance should be considered and addressed (drugs, renal disease)

If the triglycerides continue to remain high despite the aforementioned interventions, a dosage reduction of 25% of the current dose will be considered.

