In the event of an overdose of Omegaven,™ there is a risk of developing fat overload syndrome that may occur when the triglyceride level rises >200 mg/dL acutely as a result of too rapid a rate of infusion, or chronically at high infusion rates in associated with a change in the patient's clinical condition (e.g., renal

dysfunction, sepsis). In such cases, the infusion should be stopped or, if necessary, continued at a reduced dose. Metabolic acidosis has occurred in patients receiving Omegaven™ at excessive doses without simultaneous administration of dextrose.

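### The only planned triglyceride safety outcome (ever > 400 mg/dL) does not count lipid intolerance as the protocol itself defines it (> 200 mg/dL)

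*Combined protocol and SAP*

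**What the plan says.** Three places in the combined protocol and SAP set a triglyceride level.

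- **Section 10.0, Analysis of Safety and Tolerability.** Outcomes measured in both the Omegaven and the soybean group "will include whether triglycerides were ever" above 400 mg/dL. No reason is given for 400, and no other triglyceride outcome is listed. Primary safety analyses are descriptive.
- **Section 6.0, on dose changes for raised triglycerides.** The definition and what follows from it read: "If lipid intolerance develops, defined as serum triglyceride levels > 200 mg/dL, the following will be considered prior to reducing the dose". For a level taken during a continuous 24-hour infusion, the first step is: "the total dose should be infused over 20 hours, and a repeat serum triglyceride level obtained prior to resuming the infusion 4 hours later". The team is also to look for other causes. If levels stay high, the last step is: "a dosage reduction of 25% of the current dose will be considered".
- **Section 7.0, Overdose.** The warning reads: "there is a risk of developing fat overload syndrome that may occur when the triglyceride level rises >200 mg/dL acutely". The response there is: "In such cases, the infusion should be stopped or, if necessary, continued at a reduced dose".

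Table 3 in Section 6.0 schedules triglycerides at baseline and weekly for infants on Omegaven, and testing may be reduced in stable, improved patients. No triglyceride schedule or management rule is given for soybean infants. Section 10.0 also starts counting the Omegaven period 30 days after it begins, for the main analysis. It does not say whether this lag covers the triglyceride outcome.

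**The concern.** Aim 1 is the safety profile of the emulsion. For a lipid product, intolerance of the lipid load is a central part of that profile, and the protocol has already defined it. The analysis section then does not count it. It counts only a level twice as high.

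A report could therefore state that no infant exceeded the triglyceride threshold although several met the protocol's own definition of lipid intolerance and had their infusion altered because of it. A reader of the results would have no planned table showing this. The two-group comparison adds a second uncertainty: the same cut-off is applied to groups that may have been managed and sampled differently.

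**Working it through.** The plan states no sample size, event rate or triglyceride distribution for this outcome, so there is no figure to reproduce. The check sets the definitions side by side.

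**1. Ratio of thresholds.** 400 / 200 = 2.

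**2. Classification by an infant's highest measured value.**

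| Highest triglyceride | Section 6.0 | Section 10.0 |
|---|---|---|
| up to 200 mg/dL | tolerant | no event |
| above 200, up to 400 mg/dL | lipid intolerant | no event |
| above 400 mg/dL | lipid intolerant | event |

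Write p200 and p400 for the proportions ever above each level. The plan reports p400. The proportion intolerant but uncounted is p200 − p400, and the share of intolerant infants missed is 1 − p400/p200. That share can lie anywhere between 0 and 1. Nothing in the documents fixes it, so no percentage is offered.

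**3. Does another planned summary fill the middle row?** No.
- The trend models in the efficacy part of Section 10.0 concern liver function markers.
- Section 8.0 does not name raised triglycerides or lipid intolerance among the expected adverse events.
- No section plans to count intolerance episodes or triglyceride-driven changes of infusion time or dose.

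**4. Does the response above 200 affect the count above 400?** If the response prevents a fraction e of the values that would have passed 400, the observed rate is p400 × (1 − e). Any e above 0 lowers it, but e is not given and could be small:
- the steps are options to consider, not fixed actions;
- the first step applies only to levels taken on a 24-hour infusion, while Section 6.0 allows 12 to 24 hours, and it leaves the total dose unchanged;
- the 25% reduction comes last and is optional;
- with weekly sampling, the first high value seen may already exceed 400.

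The gap in step 2 exists even when e = 0.

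**5. The comparison with soybean.** The 200 mg/dL rule is written only for Omegaven. If soybean infants are managed less actively, the comparison at 400 favours Omegaven. Sampling can work the other way: an ever-above outcome can only rise with more tests, so if soybean infants are tested less often, their rate is understated. The documents settle neither point, so the net direction is unknown.

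**6. Start of counting.** If the 30-day lag applies to this outcome, rises in the first month on Omegaven are left out of the main analysis.

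**The case against.** An early level for action and a higher level for reporting marked elevation can reasonably coexist, so a mismatch alone is not an error. The Section 10.0 list is not stated to be exhaustive, the analysis is descriptive, and laboratory data go onto the case report forms. Values between 200 and 400 mg/dL are therefore recorded, not lost. This stands, and it makes the point a reporting gap. It does not close the gap: the plan does not describe 400 as a marker of severe elevation, and no planned table uses the lower level.

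A reader might go further and infer three things that the documents do not support.

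- **That the protocol's own action largely prevents the outcome.** Step 4 of the working shows why this is not established. Stopping the infusion appears only in the overdose text, and it is not clear that this text covers every value above 200.
- **That a managed group is compared with an unmanaged one.** The documents do not describe how soybean infants' triglycerides are handled, and silence in an Omegaven protocol is not evidence of no management. Section 6.0 refers to the standards of care given to all patients on parenteral nutrition. Asymmetry is possible, not shown.
- **That the size of the shortfall can be stated.** Any percentage would rest on an assumed median, spread, number of tests and within-infant correlation. The 13 infants mentioned in Section 7.0 are a count in a risk update, not a planned sample size.

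**Conclusion.** The concern holds as a gap in the planned safety reporting. The only triglyceride outcome sits at twice the protocol's own intolerance level, 400 is unexplained, and infants with peaks above 200 and up to 400 mg/dL are intolerant by definition yet uncounted. This follows from the definitions alone and needs no distributional assumption.

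Two further points hold only as possibilities: the response above 200 may work against reaching 400, by an unknown amount, and the two-group comparison at 400 may be uneven. The number of infants affected cannot be derived from the documents. The change is worth making because it is cheap and bears directly on what Aim 1 can conclude.

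**What to change.** In the safety part of Section 10.0, keep ever > 400 mg/dL, state why that level was chosen, and add, counted from the first infusion:

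1. the proportion of infants ever > 200 mg/dL, and each infant's maximum triglyceride, for the Omegaven group and, where values are available, for the soybean group, with the number of tests per infant shown in both;
2. for the Omegaven group only, the number of infants with a triglyceride-triggered change of infusion time or dose, because no such trigger is documented for soybean infants.

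Present the soybean comparison descriptively, with a caveat that management and sampling may differ. State whether the 30-day lag applies to the > 400 outcome. The triglyceride wording in Sections 6.0, 7.0 and 10.0 should be reconciled. This review takes no view on which clinical level or response is right, and the additions change none.

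The cost is a few sentences in the plan and a small amount of extra analysis. Omegaven values are already scheduled weekly. Soybean data may be incomplete, which is why the number of tests has to be reported beside them.
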